The AEs should be actively investigated, i.e. the investigator should inquire into all AE assessments that have occurred in the period since the previous evaluation, and the investigator should not expect the participant to spontaneously report any such event. The active approach is particularly true for the expected AEs. For this purpose, a specific form for registration, follow-up and closure of each adverse event in this investigation will be developed. Each AE must be completed in the form. This means that a participant may have one or more AE forms completed in a same medical evaluation, corresponding to distinct events that may have different classifications, follow-ups, and behaviors. If the participant seeks medical assistance between scheduled visits due to an AE, the investigator must proceed with appropriate medical care, record the AE on a new form (in the case of a new AE) or complete data on an AE form in progress (in the case of one not yet closed). Therefore, clinical follow-up, registration on the AE forms should not be restricted to scheduled visits. When, during the visits scheduled for the period under evaluation, no AE has occurred, the non-occurrence of AE (negative notification) should be recorded.

Every new AE record or update of an AE in progress must be updated in the database within 3 business days (except those AEs classified as severe that should be reported / updated within 24 hours), even if the event still requires monitoring and the form still needs to be updated for later closure. The investigator will follow all AEs until clinical resolution. At the end of the follow-up, the form and database should be updated one last time for information on how EA has progressed and how it has been resolved.

Some codifications will be used in the AE record for regulatory and comparison purposes. The nomenclature of AE will be according to the MedDRA dictionary (<https://www.meddra.org/how-to-use/support-documentation/portuguese>).

All AEs should be classified according to intensity as described in the qualifying intensity gradation for health conditions (WHO) [33]:

Grade 1 (Light):	A problem is present less than 25% of the time, with an intensity that a person can tolerate and that rarely occurs in the last 30 days.
Grade 2 (Moderate):	It means that a problem that is present less than 50% of the time, with an intensity that interferes in the day to day of people and that happens occasionally in the last 30 days.

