Grade 3 (Severe):	It means that a problem that is present in more than 50% of the time, with an intensity that partially alters the day-to-day of people and that happens frequently in the last 30 days.

Silimed Indústria de Implantes Ltda

[name]

[contact] [contact]

www.silimed.com.br • [contact] • facebook: silimed international/brasil

Grade 4 (Complete impairment):	It means that a problem that is present in more than 95% of the time, with an intensity that completely changes the person's day-to-day life and that occurs every day in the last 30 days.
Not specified	It means that there is not enough information to specify the intensity.
Not specified	It means that it is inappropriate to use a gradation (e.g., menstrual functions).

The investigator will use the following WHO-UMC criteria to classify the AE for causality by always having breast implants as the cause of interest [33]:

Certain / Definite:	Event or alteration (abnormal) in a laboratory examination with a plausible temporal relation to the administration of the intervention; It cannot be explained by disease or other intervention or medication; Response to discontinuation or plausible withdrawal (pharmacologically, pathologically); An event defined pharmacologically or phenomenologically (i.e., an objective and specific disorder or a pharmacologically recognized phenomenon); Satisfactory re-exposure, if necessary.
Likely:	Event or abnormal (abnormal) examination in a laboratory with a reasonable temporal relation to the administration of the intervention; Unlikely to be attributed to a disease or other intervention, medicine; Response to discontinuation or clinically reasonable withdrawal; Reexamination not required.
Possible:	Event or alteration (abnormal) in a laboratory examination with a reasonable temporal relation to the administration of the intervention; It can also be explained by illness or other interventions, medications; Information about withdrawal or discontinuation of treatment may be lacking or obscure.
Unlikely:	Event or alteration (abnormal) in laboratory examination that in relation to the moment of administration of the intervention makes an unlikely relationship (but not impossible); Sickness or other treatments subsidize plausible explanations.

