5.9. Statistical analysis plan

The statistical analysis will be divided into two parts, one descriptive and one analytical. The descriptive part will consist of showing counts and fractions of categorical variables and central tendencies (mean + standard deviation or median + interquartile range) of continuous variables recorded at the beginning of the follow-up by the groups of major interest. The groups of major interest are formed by the indication of implantation and the type of implant (primary augmentation
Silimed Indústria de Implantes Ltda

[name]

[contact] **[contact]

www.silimed.com.br • [contact] • facebook: silimed international/brasil

with textured surface implant, primary augmentation with polyurethane foam-coated surface implant). In addition, for the purpose of exploring heterogeneity this approach will also be done by participant center.

The initial statistical analysis for the analytical part is to estimate the risks (cumulative probabilities up to a follow-up time) and their respective confidence intervals of unwanted (expected and not expected) events in general and interest-specific ones (e.g. capsular contracture in the textured implants group, in the polyurethane implants group, mild events, serious events, events with probable causality, etc.), as well as events of different intensities (mild, moderate, severe, etc.). The accumulated risks up to the first events in the period of interest will be estimated through the Kaplan-Meier estimator. This analysis should consider the patient as an observation unit, and then the same approach will consider the breast as an observation unit.

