Visit 2: The following procedures will be performed – 60 days after implantation (window of + or - 30 days)

- Return of adverse event diary and evaluation of completion.
- Complete physical examination by the physician.
- Assessment and guidance on possible adverse events and conduct.
- Application of patient's and evaluator's quality of life and satisfaction questionnaires.
- Delivery of the adverse event diary and guidance on its use and completion.
- Scheduling the return to the research center, 180 days after implantation.

Visit 3: The following procedures will be performed – 180 days after implantation (window of + or - 30 days)

- Return of adverse event diary and evaluation of completion.
- Complete physical examination by the physician.
- Evaluation and guidance on possible adverse events and conduct.
- Application of patient's and evaluator's quality of life and satisfaction questionnaires.

Silimed Indústria de Implantes Ltda

[name]

[contact] [contact]

www.silimed.com.br • [contact] • facebook: silimed international/brasil

- Delivery of the adverse event diary and guidance on its use and completion.
- Scheduling the return to the research center, 365 days after deployment.

Visit 4: The following procedures will be performed – 365 days after implantation (window of + or - 30 days)

- Return of adverse event diary and evaluation of completion.
- Complete physical examination by the physician.
- Application of patient's and evaluator's quality of life and satisfaction questionnaires.
- Evaluation and guidance on possible adverse events and conduct.
- Delivery of the adverse event diary and guidance on its use and completion.
- Scheduling the return to the research center, 365 days after deployment.

Visit 5, 6, 7, 8, 9, 10, 11, and 12: The following procedures will be performed – 2, 3, 4, 5, 6, 7, 8, 9 years after implantation (window of + or - 60 days)

- Return of adverse event diary and evaluation of completion.
- Complete physical examination by the physician.
- Application of patient's and evaluator's quality of life and satisfaction questionnaires.
- Evaluation and guidance on possible adverse events and conduct.
- Delivery of the adverse event diary and guidance on its use and completion.
- Scheduling the return to the research center, 360 days after deployment.

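### Adverse event intensity grades join time, impact and frequency with no rule for when they disagree, so lasting tolerable events and short disabling events fit no grade

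*Combined protocol and SAP*

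**What the plan says.** Section 5.5.1 applies one scale to everything: "All AEs should be classified according to intensity as described in the qualifying intensity gradation for health conditions (WHO"). The grades read as follows.

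- Light (Grade 1): "present less than 25% of the time, with an intensity that a person can tolerate and that rarely occurs in the last 30 days".
- Moderate (Grade 2): "present less than 50% of the time, with an intensity that interferes in the day to day of people", and occasional in the last 30 days.
- Severe (Grade 3): "present in more than 50% of the time, with an intensity that partially alters the day-to-day of people", and frequent in the last 30 days.
- Complete impairment (Grade 4): a share above 95%, and "with an intensity that completely changes the person's day-to-day life and that occurs every day in the last 30 days".

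Two residual categories follow. One is for too little information. The other is for conditions that should not be graded at all, with menstrual functions as the example.

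The same section tells the investigator to ask about events over the whole period since the previous evaluation. In the section 6.4 visit procedures, on-site visits after year 1 fall at "2, 3, 4, 5, 6, 7, 8, 9 years after implantation (window of + or - 60 days").

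The grade is used in two places. Section 5.9 plans cumulative risks with confidence intervals for several classes of event, "as well as events of different intensities (mild, moderate, severe, etc".). Section 5.12 lists, as a data quality indicator, the number of serious, Grade 3, Grade 4 or unclassifiable events.

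**The concern.** The scale works only if persistence, impact and frequency rise together. For breast implants they often do not. Ripple, palpability, ptosis and asymmetry can be present all the time and still be tolerable. Other events can disable a woman for a few days and then resolve. Such an event can be fully documented and still meet no grade, and neither residual category describes it.

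The assessor then has to decide which element counts, and two careful assessors could decide differently while both follow the protocol. Section 5.8 provides for no masking, so the person deciding may know the implant type. The split into mild, moderate and severe would then carry information about persistence and personal practice as well as severity. That split is a planned breakdown of the primary outcome and is to be given for the textured and polyurethane groups.

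**Working it through.** The documents state no figure for this point, so there is none to reproduce. The check is on the wording of the rule.

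**Inputs (section 5.5.1)**

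| Grade | Share of time | Impact on daily life | Last 30 days |
|---|---|---|---|
| 1 | < 25% | tolerable | rare |
| 2 | < 50% | interferes | occasional |
| 3 | > 50% | partly alters | frequent |
| 4 | > 95% | completely changes | every day |

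**Step 1: two cases**

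- A tolerable ripple, always present: share 100%. It fails Grades 1 and 2 on time and Grades 3 and 4 on impact.
- A disabling event of 3 days: over 30 days the share is 3/30 = 10%. It fails Grades 3 and 4 on time and Grades 1 and 2 on impact. If the share were taken over the event's own length, it would pass the 95% test but still fail the every-day condition of Grade 4.

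**Step 2: all combinations**

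The text does not say that the percentage is a share of the 30 days; that is assumed here so that days can be counted. Each of 1 to 30 days present is crossed with the four impact levels, giving 4 × 30 = 120 combinations. The frequency words are left out, which favours the plan because they could only remove combinations.

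- Tolerable: fits on days 1–7 (7/30 = 23.3%; 8/30 = 26.7% is too long): 7.
- Interferes: fits on days 1–14 (14/30 = 46.7%; 15/30 = 50% is not below 50%): 14.
- Partly alters: fits on days 16–30: 15.
- Completely changes: fits on days 29–30 (28/30 = 93.3% is too short): 2.

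Sum: 7 + 14 + 15 + 2 = 38. So 38/120 = 32% fit a grade and 82/120 = 68% fit none. Without the 30-day assumption, the admitted share ranges give (25 + 50 + 50 + 5)/400 = 130/400 = 32.5%.

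**Step 3: a looser reading**

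Step 2 treats the impact levels as distinct. Suppose an event that partly alters or completely changes daily life is also held to meet every lower level from interferes upward. Then each of those two rows fits on days 1–14 and 16–30, which is 29 days, and the total is 7 + 14 + 29 + 29 = 79 of 120. The 3-day disabling event is now Grade 2 and is counted as moderate. The constant tolerable ripple still fits nothing.

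**Step 4: using the time element alone**

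Days 1–7 meet both Grade 1 and Grade 2, day 15 meets none, and days 29–30 meet both Grade 3 and Grade 4. The 3-day disabling event becomes Grade 1 or 2, and the constant tolerable ripple becomes Grade 3 or 4.

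**Step 5: the look-back**

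Events are sought over about 365 days between annual visits, while the grade refers to 30 days: 30/365 = 8.2%. The text does not say whether those days run back from the visit, from the report or from the event.

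**Step 6: illustration only**

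Assume a true cumulative risk of a severe event of 10%, and assume that 25%, 50% or 75% of those events last 15 days or less and so lose their severe grade. The estimate becomes 10% × 0.75 = 7.5%, 10% × 0.50 = 5.0% or 10% × 0.25 = 2.5%. With the 246 per group of section 5.10, the 95% half-width is 1.96 × √(0.10 × 0.90/246) = 3.7 points. None of these risks or shares is in the documents. Lasting tolerable events placed in Grade 3 or 4 would push the estimate the other way.

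**The case against.** The strongest reply is that the grades may be meant as typical descriptions, that the scale is attributed to a regulatory manual, and that little of importance rests on it. Much of this stands. The events of greatest interest are reoperation, removal and contracture of grade III or IV. The sample size (5.10) and the alarm limits (5.11) do not use intensity. Seriousness is defined by outcome, course of action is classified separately (5.5), and start date and duration are recorded (5.5.1), so a short severe event can still be found in the data. Whether the cited source intends a strict conjunction cannot be seen from the documents.

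A reader might infer more than the documents support in four ways.

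- That most implant events fit no grade. Of the 28 expected events listed in 5.5, about 12 are plausibly lasting states, or 43%. That is not most, it is a count of event types rather than of occurrences, and some of them may be suited to the category for ungradable conditions.
- That the 8% look-back leaves roughly nine in ten short events outside the window. This would require events to be first learned of at the annual visit. The plan also has a dated diary (5.5.2), registration outside scheduled visits (5.5.1) and participants calling in outside care (section 7).
- That slight asymmetry becomes Grade 4. It does so only if the impact element is ignored.
- That expedited reporting is compromised. Section 5.5.1 sets a 24-hour entry limit for events classed as severe, but it is unclear whether that word means intensity. Notification of serious events rests on outcome.

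The reply does not supply the missing rule. Nothing says which element prevails or which 30 days apply, and the residual categories do not cover a well-documented event whose elements conflict.

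**Conclusion.** The point holds as a defect in the grading rule. Section 5.5.1 defines each grade by three joint conditions, and lasting tolerable events and short disabling events meet none of them. The reach is limited to the cumulative risks by intensity in section 5.9 and the Grade 3 and 4 counts in section 5.12. Risks of any event, reoperation, removal, rupture and Baker-classified contracture, and serious adverse event status, do not use this grade.

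It would be tempting to conclude that the risks by intensity will be wrong by a known amount or in a known direction. The documents do not support that. Short severe events would tend to lower the severe risk, and lasting tolerable events could raise it or drop out, depending on what assessors do. The 38 of 120 describes the rule, not the events to be expected, and it rests on reading the percentage over 30 days and the impact levels as distinct.

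The change should be made, because a planned breakdown of the primary outcome depends on the grade and the repair is small.

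**What to change.** In section 5.5.1 and on the adverse event form (FORM 16), state that for the outputs in sections 5.9 and 5.12 each event is graded once, at its worst point over its whole course. The grade should use the impact element the scale already contains: tolerable, interferes with daily life, partly alters it, completely changes it. State that this element prevails over the time and frequency elements. Take persistence from the start date and duration already required on the form, and report it separately.

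If the cited scale is needed for regulatory reporting, keep it as a separate field and state which 30 days it covers.

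The cost is one added or reworded form field, and an analysis grade that no longer matches the cited scale word for word. Some judgement remains, because interfering with daily life and partly altering it are close. The fix removes the conflict between elements, not every difference between assessors.

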2.3. Expectation of expected adverse events

Technical reports provided by the FDA used for silicone breast implant registries from different manufacturers indicate a variety of risks from implant or surgery-related events. The most frequent event in all reports, consistent with the literature in general, is capsular contracture. Capsular contracture, when intense, is also the most frequent indication of implant removal. Below is a comparison of risks of events of interest by major interest groups and by different manufacturers. However, it is not possible, through the data from these reports to verify if there are differences between the different types of implants, nor what prognostic elements determine

Silimed Indústria de Implantes Ltda

[name]

[contact] **[contact]

www.silimed.com.br • [contact] • facebook: silimed international/brasil

the events in the different interest groups.

Cumulative incidence by type of event, implantation indication and implant brand (data retrieved from technical registration reports).

	Natrelle (Textured Surface - in 7 years)%		Natrelle (Textured Surface - in 3 years)%		Sientra (any surface - in 3 years)%		Mentor (any surface - in 3 years)%	
Event	Augmentation	Reconstruction	Augmentation	Reconstruction	Augmentation	Reconstruction	Augmentation	Reconstruction
Any Complication	31,0	53,0	-	-	-	-	-	-
Any Reoperation	22,4	45,2	12,7	21,0	12,6	34,9	15,4	27,0
Removal of the implant with or without replacement	12,6	29,3	-	-	-	-	-	-
Removal of the implant without replacement	1,2	5,3	0,5	2,9	1,2	7,0	2,3	5,7
Removing the Implant with Replacement	11,5	25,2	5,0	14,9	4,6	19,1	2,8	7,4
Capsular contracture grade III / IV	6,1	10,7	2,1	7,3	6,0	8,8	8,1	8,3
Implant rupture	6,9	8,9	1,3	0,0	3,0	0,0	0,0	0,0

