5.5. Primary Outcomes

Primary outcomes will be the adverse events of the participants. Below is a section on the safety, monitoring, and classification of adverse events. The project foresees the classification of **Silimed Indústria de Implantes Ltda**

adverse events according to severity, intensity, causality, type (tissue-related, aesthetic or implant-related events) and according to the course of action for the solution of the event (e.g. unnecessary additional treatment, additional surgical treatment, surgical treatment without explantation and surgical treatment with explantation).

The events related to the tissue are the events that can occur following any breast surgery. Aesthetic events are primarily aesthetic and related to the presence of the implant (e.g., ripples, wrinkles, etc.). Events related to the implant are those that are specifically assigned to the presence of the implant (e.g., capsular contracture, implant rupture, etc.).

The adverse events can be defined as any medical event, yet the literature points to some occurrences as more frequent or as expected, since they are events observed in previous studies and their incidence has already been estimated in these studies. Below is a list of events recorded in previous studies that are considered as expected adverse events:

- Anesthesia: loss of local sensitivity, booth for pain and other sensations, usually reported by the patient during the medical evaluation.
- Asymmetry: after implantation, the breasts do not look identical or have a dissimilar appearance when both sides of a central line are compared for shape, size, level, or location.
- Tissue atrophy: thinning or shrinking of the skin, usually detected on inspection.
- Calcification of the capsule: deposits of calcium salts in the capsule or as a thin layer around the implant. Calcification may be local or diffuse and is usually asymptomatic, occasionally detected when an image of the chest (e.g. radiography or MRI) is performed for investigation of other health conditions.
- Cyst (requiring biopsy or removal): Cyst is a closed structure, such as a sac or bladder, formed in tissues, containing fluid or semi-fluid in its interior. May or may not have a calcified capsule. It can be identified by physical examination and medical evaluation if it is superficial, or by imaging tests (e.g. radiography or tomography)

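### The causality scale has no rule for an implant left in place, so the planned risk of probably related events can depend on explantation

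*Combined protocol and SAP*

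**What the plan says.** Section 5.5.1 tells the investigator to "classify the AE for causality by always having breast implants as the cause of interest", using a WHO-UMC scale cited to the regulator's manual for device trials. Certain includes "Response to discontinuation or plausible withdrawal (pharmacologically, pathologically" and, as a conditional item, "Satisfactory re-exposure, if necessary". Likely includes "Unlikely to be attributed to a disease or other intervention, medicine; Response to discontinuation or clinically reasonable withdrawal; Reexamination not required". Possible is the graded level that tolerates missing or unclear information on withdrawal, but it also describes an event for which another illness or treatment is a candidate explanation. Nothing in 5.5.1 adapts these items to an implant that stays in place.

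Section 5.9 uses the grade. Its examples of event groups whose Kaplan-Meier cumulative risk will be estimated with confidence intervals include "mild events, serious events, events with probable causality, etc".

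Section 5.5 treats causality, type of event and course of action as separate classifications. On type it says: "Events related to the implant are those that are specifically assigned to the presence of the implant (e.g., capsular contracture, implant rupture, etc". Explantation is one of its courses of action, and its event list treats removal as a consequence of an earlier adverse event.

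**The concern.** The scale is worded for a treatment that can be stopped, where improvement on stopping is evidence of cause. A breast implant is withdrawn only by surgery, and removal is a treatment decision, not a test of cause. If Likely needs a response to withdrawal, the probable-causality risk mixes two things: whether the implant caused the event, and whether it was taken out. The estimate would then be too low. A difference in removal practice between the textured and polyurethane groups could also appear as a difference in probable risk at equal true risk. Implant type is chosen by the attending physician (5.7) and assessment is unmasked (5.8), so unequal removal practice cannot be excluded.

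**Working it through.** The plan states no figure for this quantity, so there is none to reproduce. The check is a comparison of definitions, followed by an illustration of size.

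**1. Definitions side by side (5.5.1, paraphrased)**

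| Item | Certain | Likely | Possible |
|---|---|---|---|
| Time relation | plausible | reasonable | reasonable |
| Other cause | ruled out | improbable | also a candidate |
| Response to withdrawal | listed, no waiver | listed, no waiver | may be missing |
| Re-exposure | only if needed | waived (printed as re-examination) | not mentioned |

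The scale says where an item may be absent, and for withdrawal it says so only under Possible.

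**2. Test case.** Take a grade III contracture with a reasonable time relation, no other cause found and the implant kept. It meets two Likely items and lacks the withdrawal item. It fits Possible on timing and on missing withdrawal data, but not on an alternative explanation. It does not fit Unlikely. It has no clean class, and two assessors could grade it differently.

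Explantation does not guarantee that the item can be assessed: 6.5.1 lists removal or replacement among the reasons a participant may be withdrawn from the study.

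**3. Illustration of size.** The inputs are from the table in 2.3, Natrelle textured, augmentation, seven years: any complication 31.0%; "Removal of the implant with or without replacement" 12.6%. I assume both rows count women on the same basis.

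- Women with a complication and no removal ≥ 31.0 − 12.6 = 18.4 points.
- As a share of women with a complication: 18.4/31.0 = 59%.
- In an uncensored arm of 350: 350 × 0.310 = 108.5 with a complication, 350 × 0.126 = 44.1 with removal, and a difference of 64.4.

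Counting every removal as following a complication, and removal with replacement as withdrawal, both keep this bound low.

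Let q be the share of women with a complication whose event truly merits Likely or higher. Assume that this is unrelated to removal and that every removal followed a complication. True risk = 31.0q; gradable risk on the literal reading = 12.6q.

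| q (assumed) | True risk | Gradable risk |
|---|---|---|
| 0.25 | 7.75% | 3.15% |
| 0.50 | 15.5% | 6.3% |
| 1.00 | 31.0% | 12.6% |

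The documents do not give q.

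**4. Contracture alone.** The lower bound on the share of grade III/IV contractures without removal is (contracture − all removals)/contracture, set to zero if negative. Augmentation columns of the same table:

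- Mentor, 3 years: (8.1 − (2.3 + 2.8))/8.1 = 3.0/8.1 = 37%.
- Sientra, 3 years: (6.0 − (1.2 + 4.6))/6.0 = 0.2/6.0 = 3%.
- Natrelle, 3 years: 2.1 against 0.5 + 5.0 = 5.5, so 0%.
- Natrelle, 7 years: 6.1 against 12.6, so 0%.

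The bound runs from 0% to 37% and does not settle the size for contracture.

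**5. Comparison between implant types.** Suppose both groups have the same true probable risk R, and shares a and b of the affected women are explanted. The gradable risks are Ra and Rb, and their ratio is a/b whatever the value of R. The documents give neither a nor b.

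**The case against.** The strongest reply is that 5.5.1 never says every listed item must be met. A reader might infer that an event with a retained implant can never rate above Possible, but the documents do not support a fixed ceiling. Strict matching excludes Possible too when no other cause exists, and best-fit judgement could place the event in Likely. This stands. What remains is that the handling is unspecified and grading may not be uniform.

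A reader might also infer that 5.5 and 5.5.1 contradict each other on contracture and rupture. They do not: type sorts kinds of event, while causality grades the individual case. Ripples and wrinkles are typed as aesthetic in any case.

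It is also tempting to read 59% or 37% as the understatement itself. Neither is. The 59% bounds retained implants among all complications, many of which might not merit Likely. The 37% is the largest of four column results; the Sientra trial implants, which the bibliography describes as Silimed brand, give about 3%.

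Nothing in the documents shows that one implant type is explanted more readily, so the between-group bias is conditional. The regulator's manual and the content of FORM 16 are not available here and may contain guidance.

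Finally, the consequence is narrow. Probable causality is one example in an open list in 5.9. The sample size (5.10) and alarm limits (5.11) use event types, and notification of unexpected serious events starts at Possible. This also stands.

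**Conclusion.** The gap is real and limited. As written, the scale ties Likely and Certain to a response that a woman who keeps her implant cannot show, and no rule says what to do then. Applied literally, the probable-causality risk in 5.9 depends on explantation and is biased downward. The direction follows from the definitions; the size does not. The 59% rests on another manufacturer's seven-year data and describes implant retention, not misgrading. I take probable in 5.9 to mean the Likely level of 5.5.1 or higher.

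All-event, event-specific, seriousness, intensity and alarm analyses do not use this grade. Nor does the gap remove events from notification. The plan's main safety estimates are therefore not in question.

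**What to change.** In 5.5.1 and on FORM 16, state that the withdrawal item is not applicable while the implant remains in place. Likely is then met by a reasonable time relation and an event unlikely to be attributed to another cause. In 5.9, report cumulative risks for possible-or-higher beside probable-or-higher, by implant type, so that readers can see how far the result depends on grading.

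This needs rewording, form guidance and one extra set of estimates, with no added procedures. The downside is a small departure from the cited scale, which needs a mapping note in regulatory reports. If grading has already begun, events graded so far should be checked once against the new rule.
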